## **4.0 Secondary Aims Data Analysis**

**4.1 Secondary Aim 1 Analysis (a):** *Analysis of the contribution of "standard of care" methods of anesthesia (general vs regional neuraxial anesthesia) on clinical effectiveness of three different prophylaxis regimens.* To address this aim, we will compare those with general to those with regional anesthesia with respect to risk of the clinical and patient-reported outcomes, overall, and in strata defined by treatment. To assess whether the impact of treatment on outcomes varies by anesthesia type, we will fit longitudinal regression models with interaction terms between treatment and anesthesia type. These models will include random effects for patient and surgeon to account for correlation between repeated measures on the same patient and surgeon. For the binary events in time (e.g., our primary composite outcome for Aim 1), this will be assessed using a Cox regression model with an identity link, censoring patients at the time of loss to follow-up or treatment switch. The interaction terms in this model will represent the difference in the treatment group risk differences between those on general and those on regional anesthesia. The p-values for these terms will provide a measure of the strength of evidence of a difference in treatment effect by anesthesia. We will also adjust for covariates such as age, baseline comorbidities, and surgery type by including them in the model if they appear to confound the relationship between anesthesia and outcomes. Standard errors of estimates in the model will be calculated using a robust variance estimate to account for the clustering within patients and surgeons. We are accounting for clustering by surgeon in the analysis because anesthesia methods may vary by surgeon, so we need to adjust for surgeon.

**4.2 Secondary Aim 2 Analysis (b)** *Analysis of the relative frequency of thromboembolic events and bleeding complications between hip and knee replacement patients with each of the three regimens.* We will use the methods described above for Aims 1-3 separately for knee and hip patients. Formal assessment of whether event rates or the impact of the treatments differ between those provided knee or hip replacement will be performed using Cox regression with interaction terms between treatment and operation type.

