## **5.0 Power and Precision**

**5.1 Sample Size.** We expect to recruit 20,000 participants. Conservatively assuming 10% of them will not be evaluable, we expect to have data on 18,000 patients. It is estimated that 5% of the patients will be ineligible for aspirin,

2% will be ineligible for rivaroxaban and 1% will be ineligible for Warfarin. It is also estimated (based on the first 6 months of data) that 2.5% of those assigned to aspirin will not be treated with aspirin, 6.4% of those assigned to warfarin will not be treated with warfarin, and 13.6% of those assigned to rivaroxaban will not be treated with rivaroxaban. These patients will be excluded from the primary analysis. Therefore, with a total sample of approximately 20,000, we project that there will be 7239, 7223, and 5389 patients assigned to and treated with aspirin, Rivaroxaban, and Warfarin groups, respectively. We expect to have six-month outcome data on the vast majority of the patients, so we based our precision and power calculations on a binary outcome.

**5.2 Precision of Estimates.** The primary endpoint is a composite consisting of the occurrence of death from any cause and clinically evident PE or DVT. For an observed endpoint that occurs 1.1% of the time, considering the cross-over rates and conservatively assuming that 10% of those randomized will not have surgery or will be lost to follow-up, the margin of error of our estimates of risk will be 0.27%, 0.30%, and 0.35% for aspirin, rivaroxaban, and warfarin. Clinically significant bleeding is expected to occur in 0.5-1% of patients on aspirin, 4-5% of patients on rivaroxaban, and 1-2% of patients on warfarin. Given those percentages, the margin of error for estimates of bleeding risk will be 0.22%, 0.61%, and 0.41%, respectively.

**5.3 Power to confirm non-inferiority.** The adoption of a non-inferiority methodology for this trial was predicated on establishing the non-inferiority of aspirin, as compared to either warfarin or rivaroxaban, in preventing death and thromboembolic disease with the assumption that aspirin would very likely result in fewer bleeding complications than either of these two agents. The statistical test of non-inferiority will be based on only those who were medically or logistically eligible for randomization to either of the two groups being compared. Table 1 shows the power to detect non-inferiority for the comparison of aspirin to warfarin with no additional patients randomized to warfarin.

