**Table 1. Numbers of patients and resulting power and precision in comparing aspirin to warfarin.**

	Aspirin	Warfarin
Number Randomized as of May 1, 2023	5132	5389
Number Eligible for both treatments (either medically or due to logistics)	4703	4698
Projected number who took the assigned treatment 	4402	3688
Projected number who will have complete follow-up 	3962	3319
Projected width of the 95% CI for the difference in risk of primary outcome	0.96 percentage pts	
Power to obtain evidence of non-inferiority based on 0.69% margin of inferiority	80.3%	
Margin of inferiority detectable with 80% power	0.69 percentage pts	

Based on a crossover rate of 21.5% and 6.4% for Warfarin and Aspirin, respectively.

Assuming that 90% of those randomized have surgery, do not withdraw, and have 6-month follow-up information.

**Recruitment and randomization.** To achieve the total of approximately 18,000 evaluable patients we will recruit approximately 20,000 to accommodate the possibility of 10% loss to follow-up. We will randomize patients with equal probabilities to each of the three regimens using a web-based program provided by Statix. Those sites that are on the restricted randomization plan due to structural barriers will randomize patients using a 1:1 randomization scheme. Following removal of warfarin from the protocol in June 2023, all sites will randomize patients using a 1:1 scheme to either aspirin or rivaroxaban. The web application is available 24/7, password protected, and maintains an audit trail of transactions with time stamp login for users. There will be a separate randomization schedule for each clinical site, stratified according to operation (hip or knee) to ensure balanced intervention groups with respect to site and operation. Within each stratum, assignments will be randomly permuted within repeating blocks of varying size.

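### Section 4.1 says the anesthesia analysis must adjust for surgeon, but its event model handles surgeon only through a robust variance, so between-surgeon risk differences stay in the general-versus-regional comparison

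*Protocol*

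**What the plan says.** Protocol section 3.1.3 (Data Analysis), item 4.1, covers Secondary Aim (a), the contribution of anesthesia type. Its elements are:

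- **The comparison.** "we will compare those with general to those with regional anesthesia with respect to risk of the clinical and patient-reported outcomes", overall and by treatment. Anesthesia type is not randomised.
- **Longitudinal models.** They carry treatment-by-anesthesia interactions, and "These models will include random effects for patient and surgeon to account for correlation between repeated measures on the same patient and surgeon".
- **Event outcomes**, such as the Aim 1 composite: "this will be assessed using a Cox regression model with an identity link". P-values are described for its interaction terms.
- **Covariates.** "We will also adjust for covariates such as age, baseline comorbidities, and surgery type by including them in the model", on condition that they appear to confound the relationship between anesthesia and outcome. Surgeon is not in the list.
- **Variance.** "Standard errors of estimates in the model will be calculated using a robust variance estimate to account for the clustering within patients and surgeons".
- **Rationale.** "We are accounting for clustering by surgeon in the analysis because anesthesia methods may vary by surgeon, so we need to adjust for surgeon".

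The Recruitment and randomization paragraph under section 5.0 stratifies by site and by hip or knee operation. Neither surgeon nor anesthesia type is a stratum.

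**The concern.** If anesthesia choice varies by surgeon, and surgeons also differ in patient mix or local practice, surgeon confounds the anesthesia comparison. The last sentence of 4.1 recognises this and then treats the clustering correction as the answer. Clustering and confounding are different problems. A sandwich variance allows for patients of one surgeon resembling each other. It does not move the coefficient, which still blends the contrast within surgeons with the contrast between general-favouring and regional-favouring surgeons.

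At stake is the descriptive message on anesthesia and event risk. A difference between surgeons could be reported as a difference between anesthesia types, in an analysis whose text says surgeon has been adjusted for.

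**Working it through.** The protocol gives no power or error rate for this analysis, so there is no figure to reproduce. The check is a reading of the text plus an illustration of size.

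**1. Stated aim against stated tool (section 4.1)**

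| Model | Surgeon in the mean model? | Surgeon in the variance? |
|---|---|---|
| Longitudinal | Random effect, given for correlation | Yes |
| Event (Cox) | None stated | Robust variance |

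**2. Inputs.** From the protocol: 18,000 evaluable patients (5.1) and a 1.1% composite risk (5.2: "For an observed endpoint that occurs 1.1% of the time"). As in 5.1, a binary six-month outcome stands in for time to event. All surgeon-level inputs below are assumptions. The true anesthesia effect is set to zero.

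**3. Closed-form illustration.** Let surgeon share of general anesthesia *p* follow Beta(0.7, 0.7), and let surgeon risk be 0.011 + *g*(*p* − 0.5).

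- Var(*p*) = 0.7 × 0.7 / (1.4² × 2.4) = 0.104. The variance of the individual anesthesia indicator is 0.25.
- Expected estimate with no surgeon term = *g* × 0.104 / 0.25 = 0.417*g*. For *g* = 0.5 points this is 0.21 points; for *g* = 1.0 it is 0.42 points. The true value is 0.
- Standard error = √[0.011 × 0.989 / (18,000 × 0.25)] = 0.155 points.
- Approximate false rejection at two-sided 5%: Φ(0.208/0.155 − 1.96) = Φ(−0.62) = 27%, and Φ(0.417/0.155 − 1.96) = Φ(0.73) = 77%.

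Simulation of the same set-up (600 replicates; 100 or 250 surgeons) agrees:

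| Gradient *g* (points) | Estimate, robust variance only (points) | Robust SE | False rejection | Within-surgeon estimate (points) | False rejection |
|---|---|---|---|---|---|
| 0 | −0.01 to 0.00 | 0.154-0.155 | 5.5-6.2% | −0.01 to 0.00 | 4.0-6.7% |
| 0.5 | 0.21 | 0.155-0.156 | 26-28% | 0.00 to 0.01 | 3.5-6.2% |
| 1.0 | 0.41-0.43 | 0.157-0.159 | 72-79% | −0.01 to 0.01 | 3.5-6.7% |

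The naive SE was 0.155-0.156, so clustering the variance gave almost no protection.

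**4. Correlation-based illustration.** Assumptions: 100-200 surgeons, logit SD 1.5 for use of general anesthesia, surgeon log-risk SD 0.3-0.5, and correlation *r* between the two.

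- Robust variance only: about 4-7% false positives at *r* = 0, 8-21% at *r* = 0.3 and 16-46% at *r* = 0.5. The bias is 0.09-0.31 points for *r* of 0.3-0.5.
- With the surgeon's share of general anesthesia as a covariate, or surgeon fixed effects: 5-7%, with bias about 0.
- A repeat with an assumed surgeon structure gave 0.10-0.28 points and 11-38% when surgeon risk was correlated with anesthesia use, against about 0 and 4-7% with a surgeon term.
- At an assumed 2.5% bleeding risk and *r* = 0.3: 16-30%, against about 6%.

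**5. The interaction.** Adding randomised treatment to the set-up in step 4, with robust variance and no surgeon term, the treatment-by-anesthesia interaction had bias of −0.01 to +0.02 points and 4.7-6.0% false positives. The repeat gave about 3-8% with bias near 0. Bias appeared only when the drug effect was also made to vary by surgeon in step with anesthesia use.

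**The case against.** **The text leaves room.** It states the need to adjust for surgeon, its covariate list is open-ended, and the form of a surgeon term could be left to a statistical analysis plan that is not shown. Missing detail alone would be no finding. Here, though, the protocol names both a method and a reason, and the method does not serve the reason. An analyst who followed 4.1 could fairly stop at the robust variance.

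**The random effects might be meant for the Cox model too.** The sentence is attached to the longitudinal models and gives correlation of repeated measures as its purpose. The event model then gets a robust variance and no frailty. A surgeon random effect would in any case remove between-surgeon confounding only in part.

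**The size is assumed.** This stands. The protocol gives no number of surgeons, spread of anesthesia use or link to surgeon risk, and with no link the planned method behaves properly. The simulations also omit the planned patient-level covariates, which could absorb some case mix.

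**The remedy works by construction.** This stands in part. In the simulations anesthesia depends on surgeon alone, so a within-surgeon contrast must be unbiased. In practice, choice by patient condition within a surgeon's list would remain as confounding.

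**Stronger readings.** A reader might infer that the treatment-by-anesthesia interaction is equally compromised. It is not: treatment is randomised within site and operation, so surgeon differences in baseline risk largely cancel from the drug contrast. A reader might also infer that a misleading p-value is planned for general versus regional anesthesia, or that this is the only analysis of the aim. Section 4.1 describes p-values only for the interaction terms, and it also has patient-reported-outcome models with surgeon effects.

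**Conclusion.** The point holds for the non-randomised general-versus-regional comparison of event risk, overall and within treatment groups. The stated handling of surgeon does not deliver the adjustment that 4.1 says is needed. That a robust variance leaves the estimate unchanged does not depend on any assumption; the size of the resulting bias does. It ranges from none, if surgeon risk is unrelated to anesthesia use, to about 0.1-0.3 points on a 1.1% risk with roughly 8-46% false positives at correlations of 0.3-0.5. Steeper assumed gradients give more.

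The interaction is exposed only if the drug effect itself varies across surgeons in step with their anesthesia use. The aim is secondary, and the documents give no ground for carrying the point over to the primary aims or any randomised comparison. It is worth correcting because the protocol already accepts the need and the change is small.

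**What to change.** In the section 4.1 event model used for the general-versus-regional comparison, overall and by treatment:

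1. Put surgeon into the mean model, through surgeon strata or fixed effects, or with each surgeon's proportion of general anesthesia as a covariate. The last suits sparse data: 18,000 × 1.1% = 198 events, or about one to two per surgeon if there are 100-200 surgeons.
2. Keep the surgeon-clustered robust variance and the planned patient-level covariates.
3. Reword the closing sentence so that the robust variance handles correlation and the surgeon term handles confounding.
4. Report the comparison as observational, since confounding by indication within surgeons remains.

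Adding the product of surgeon proportion and treatment to the interaction model is an optional sensitivity analysis.

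The cost is one variable derived from surgeon and anesthesia type, a few lines of text and some precision. The standard error of the anesthesia effect rose by about 10-20% under the assumptions of step 4. Under the wider spread of anesthesia use in step 3 it rose by about 30%: √[0.25 / (0.25 − 0.104)] = 1.31, or 0.155 to about 0.20 points.

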## **5.0 Power and Precision**

**5.1 Sample Size.** We expect to recruit 20,000 participants. Conservatively assuming 10% of them will not be evaluable, we expect to have data on 18,000 patients. It is estimated that 5% of the patients will be ineligible for aspirin,

2% will be ineligible for rivaroxaban and 1% will be ineligible for Warfarin. It is also estimated (based on the first 6 months of data) that 2.5% of those assigned to aspirin will not be treated with aspirin, 6.4% of those assigned to warfarin will not be treated with warfarin, and 13.6% of those assigned to rivaroxaban will not be treated with rivaroxaban. These patients will be excluded from the primary analysis. Therefore, with a total sample of approximately 20,000, we project that there will be 7239, 7223, and 5389 patients assigned to and treated with aspirin, Rivaroxaban, and Warfarin groups, respectively. We expect to have six-month outcome data on the vast majority of the patients, so we based our precision and power calculations on a binary outcome.

**5.2 Precision of Estimates.** The primary endpoint is a composite consisting of the occurrence of death from any cause and clinically evident PE or DVT. For an observed endpoint that occurs 1.1% of the time, considering the cross-over rates and conservatively assuming that 10% of those randomized will not have surgery or will be lost to follow-up, the margin of error of our estimates of risk will be 0.27%, 0.30%, and 0.35% for aspirin, rivaroxaban, and warfarin. Clinically significant bleeding is expected to occur in 0.5-1% of patients on aspirin, 4-5% of patients on rivaroxaban, and 1-2% of patients on warfarin. Given those percentages, the margin of error for estimates of bleeding risk will be 0.22%, 0.61%, and 0.41%, respectively.

**5.3 Power to confirm non-inferiority.** The adoption of a non-inferiority methodology for this trial was predicated on establishing the non-inferiority of aspirin, as compared to either warfarin or rivaroxaban, in preventing death and thromboembolic disease with the assumption that aspirin would very likely result in fewer bleeding complications than either of these two agents. The statistical test of non-inferiority will be based on only those who were medically or logistically eligible for randomization to either of the two groups being compared. Table 1 shows the power to detect non-inferiority for the comparison of aspirin to warfarin with no additional patients randomized to warfarin.

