The proposed study period will now encompass approximately 10 years: 9 mos for preliminary work; 97 months of patient enrollment; 6 mos trailing follow-up after closure of enrollment; and 6 mos final data analysis. Each site will enroll approximately 1,000 patients over three years for an average annual site enrollment of 333 patients. Each site will aim to reach this goal of 1,000 patients with recruitment continuing at all sites until the overall study enrollment goal is met. With anticipation of no more than a 10% rate of loss to follow-up, which is a conservatively high number in this elective patient population with planned lifetime follow-up, the study will result in enrollment of 18,829 patients with complete follow-up for primary outcome endpoints in approximately 18,000. Nevertheless, a concerted and proactive effort will be required to capture outcome assessment data consistently at the pre-specified time points. We will recruit patients locally within the geographic region of each participating institution to the practices of all participating surgeons in those institutions. Regional advertisement of the trial will assist in recruitment as will the fact that the trial involves only FDA approved drugs endorsed by current clinical guidelines without use of any “experimental” agents. National patient advocacy organizations involved as stakeholders in the trial will assist in publicizing trial recruitment and results.

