## **4. Protection of Human Subjects**

### **4.1. Risks to the Subjects**

#### **4.1.1. Human Subjects Involvement and Characteristics**

All patients 21 years of age or older who elect to undergo total hip or knee replacement as treatment of end-stage arthritic disease will be eligible for recruitment and enrollment.

The characteristics of the subject population will reflect the characteristics of the general population undergoing total joint replacement; ages will range from mid-30s to mid-80s, and of a general health status that would allow medical clearance for an elective major orthopaedic surgical procedure. We anticipate enrollment of approximately 25,000 patients. Consecutive patients of participating surgeons at a goal of 25 selected institutions under the direction of the field site PI will be recruited and asked to consider enrollment in the study, as noted previously in section 3.1.2a. Recruitment and retention benefits to the subjects include enhanced awareness of prevention, diagnosis, and treatment of standard thromboembolic complications of total joint replacement procedures. Stratified randomization will occur for patients who have a medical contraindication to use of any one or two of the three study prophylaxis regimens for venous thromboembolism employed in the trial as well as for patients at those sites using a restricted randomization scheme due to fixed structural barriers. Exclusion criteria include a preoperative need for chronic anticoagulation other than with antiplatelet medications, a known condition of thrombophilia proven by diagnostic laboratory testing, or any of the criteria previously stipulated in section 3.1.2 (c). No prisoners or other vulnerable patient populations will be included in the study.

It is anticipated that gender of the study participants will reflect that of the general population with arthritic disease, having a slight predilection for women over men by approximately 55% to 45%. Racial and ethnic diversity will reflect the location and socioeconomic nature of the participating sites, a majority of which are urban academic health centers. This fact ensures the quality of the clinical trial infrastructure as well as a balance of urban and rural locations that will preferentially include under-represented racial and ethnic minorities served by these safety net institutions.

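### Section 5.1 gives a randomised count as the number treated as assigned (certain for warfarin, very probable for aspirin and rivaroxaban), and its crossover rates are not reconciled with Table 1 or with the Section 5.2 margins

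*Protocol*

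**What the plan says.** Protocol Section 5.1 starts from a recruitment target: "We expect to recruit 20,000 participants". It takes off 10% as not evaluable, giving 18,000. From the first 6 months of data it then gives the share not treated as assigned: 2.5% for aspirin, 13.6% for rivaroxaban, and for warfarin "6.4% of those assigned to warfarin will not be treated with warfarin". It excludes these patients from the primary analysis and draws the consequence: "we project that there will be 7239, 7223, and 5389 patients assigned to and treated with aspirin, Rivaroxaban, and Warfarin groups, respectively".

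Table 1 in Section 5.3 covers aspirin against warfarin with the warfarin arm closed. Its first row, "Number Randomized as of May 1, 2023", reads 5132 for aspirin and 5389 for warfarin. Its first footnote reads "Based on a crossover rate of 21.5% and 6.4% for Warfarin and Aspirin, respectively".

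Section 5.2 takes a 1.1% endpoint risk, says that it allows for crossover and 10% loss, and concludes that "the margin of error of our estimates of risk will be 0.27%, 0.30%, and 0.35% for aspirin, rivaroxaban, and warfarin".

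Enrolment is also given differently elsewhere. Section 3.1 says "the study will result in enrollment of 18,829 patients with complete follow-up for primary outcome endpoints in approximately 18,000", and Section 4.1.1 says "We anticipate enrollment of approximately 25,000 patients".

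**The concern.** The primary analysis is per-protocol in the protocol's own sense: a patient never treated as randomised is left out, and one who switches later is censored at the switch. The treated-as-assigned count in each arm is therefore the starting size of the primary analysis set, and Section 5.1 is where the protocol states it.

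The same 5389 cannot be both everyone randomised to warfarin and those left after crossovers are removed, at 6.4% or at 21.5%. The figure 6.4% is also warfarin's rate in one place and aspirin's in the other. A reader cannot tell how large the primary analysis set is expected to be. Nor can the reader tell what crossover to expect in the rivaroxaban arm, which is in the only comparison still being randomised.

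**Working it through.** **Inputs.** Counts 7239 / 7223 / 5389 for aspirin / rivaroxaban / warfarin, and crossover 2.5% / 13.6% / 6.4% (Section 5.1). Randomised 5132 aspirin and 5389 warfarin, eligible for both 4703 and 4698, crossover 6.4% and 21.5%, follow-up 90% (Table 1). Risk 1.1% and margins of error 0.27 / 0.30 / 0.35% (Section 5.2). Non-inferiority margin 0.69 points (Section 1.2 of the analysis plan and Table 1). The alpha of the one-sided test is not stated; 0.025 is assumed because it reproduces Table 1, whereas 0.05 would give 87.8%.

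**1. Table 1 reproduces.**
- Treated as assigned: 4703 × 0.936 = 4402; 4698 × 0.785 = 3688.
- With follow-up: 4402 × 0.9 = 3962; 3688 × 0.9 = 3319.
- SE = √[0.011 × 0.989 × (1/3962 + 1/3319)] = 0.002454. CI width = 2 × 1.96 × SE = 0.96 points. Power = Φ(0.0069/SE − 1.96) = 80.3%.

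With Section 5.1's rates the same table would give 4127 and 3958 patients, power 84.5% and width 0.91 points, so the choice of rates matters.

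**2. The Section 5.1 counts do not reproduce as treated counts.**
- Sum: 7239 + 7223 + 5389 = 19,851.
- Dividing each count by (1 − crossover) gives the number that would have to be randomised: 7425 + 8360 + 5757 = 21,542 on Section 5.1's rates, or 7734 + 8360 + 6865 = 22,959 with Table 1's rates for aspirin and warfarin. Both exceed 20,000, and both need more warfarin patients than the 5389 randomised.
- With 20,000 recruited, warfarin fixed at 5389 and the rest split equally, each other arm has (20,000 − 5389)/2 ≈ 7305. With no crossover removed, all three stated counts lie within 3% of this split. With Section 5.1's crossovers removed it becomes 7123 / 6312 / 5044, and only aspirin is within 3%.

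**3. Crossovers removed like for like** (stated count × (1 − crossover), no loss to follow-up applied).

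| Rates | Aspirin | Rivaroxaban | Warfarin | Total | Excess in 5.1 |
|---|---|---|---|---|---|
| Section 5.1 | 7058 | 6241 | 5044 | 18,343 | 1,508 |
| Table 1 (rivaroxaban 13.6%) | 6776 | 6241 | 4230 | 17,247 | 2,604 |

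**4. Section 5.2 margins** (1.96 × √[0.011 × 0.989/n]).

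| n used | Aspirin | Rivaroxaban | Warfarin |
|---|---|---|---|
| Section 5.1 counts as stated | 0.24% | 0.24% | 0.28% |
| Section 5.1 rates, then × 0.9 | 0.26% | 0.27% | 0.30% |
| Table 1 rates (rivaroxaban 13.6%), then × 0.9 | 0.26% | 0.27% | 0.33% |
| Table 1 final row (3962, 3319) | 0.32% | not given | 0.355% |
| Stated | 0.27% | 0.30% | 0.35% |

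The warfarin margin matches Table 1's 3319. So does its bleeding margin of 0.41%, at 1.5%, the midpoint of the stated 1-2% (calculated 0.414%). Aspirin and rivaroxaban match no row. Allowing for rounding (0.295 to 0.305%), the rivaroxaban margin implies about 4,490 to 4,800 patients. Against 7223 × 0.9 = 6501, that is 26 to 31% crossover, where Section 5.1 states 13.6%.

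**5. Aspirin-rivaroxaban power** (same formula and assumptions as step 1).
- n = 6352 and 5617 (Section 5.1 rates, × 0.9): 95.1%.
- n = 6098 and 5617 (Table 1 aspirin rate, × 0.9): 94.7%.
- n = 5733 and 4644 (implied by the 0.27% and 0.30% margins): 91.8%.

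These do not apply the restriction to patients who could have received either drug, which is not given for this pair. As an illustration, applying Table 1's warfarin ratio (4698/5389 = 0.872) to both arms in the last case gives n = 4998 and 4049, and 87.9%.

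**6. Enrolment.** 18,829 × 0.9 = 16,946, not about 18,000; 18,000 would need 95.6% completeness.

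**The case against.** The strongest reply is that nothing downstream uses the Section 5.1 counts. Table 1 begins from its own numbers, applies crossover and follow-up, and reproduces. The Section 5.2 margins correspond to smaller samples than Section 5.1 states and are wider for it. This stands: the misstatement does not reach any stated power or precision figure.

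A second reply is that the two sets of rates come from different data cuts. Section 5.1 dates its rates to the first 6 months, whereas Table 1 uses counts as of May 1, 2023. That is plausible, but the protocol does not date Table 1's rates or say that they replace the others, and both stand as current text.

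A third reply is that only the warfarin count is directly shown to be a randomised count. This also stands. For aspirin and rivaroxaban it is an inference from the sum and from the failed reproduction, and aspirin's 2.5% is too small to settle that arm alone.

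A reader might also take the overstatement to be larger, by taking off the 10% loss as well or by comparing with 18,000. The document does not support that. Section 5.1 does not present these counts as net of follow-up loss, patients with incomplete follow-up are censored and not dropped, and 18,000 is the evaluable total before crossovers.

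**Conclusion.** Section 5.1 is wrong as written. The warfarin 5389 is the randomised count; treated as assigned it would be 5044 (6.4% crossover) or 4230 (21.5%). If the other two counts are also randomised counts, which is very probable, the stated total of 19,851 is too high by 1,508 to 2,604. The lower figure rests on Section 5.1's rates. The upper rests on Table 1's rates for aspirin and warfarin, with 13.6% kept for rivaroxaban.

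The crossover rates are unreconciled, and the aspirin and rivaroxaban margins in Section 5.2 cannot be derived from the stated inputs. The current rivaroxaban crossover rate is the main unknown.

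A reader might infer an underpowered trial. The document does not support this: Table 1's 80.3% holds, and aspirin-rivaroxaban power is about 92 to 95% at 1.1% risk in both arms and one-sided 0.025 (assumed), before any pairwise eligibility restriction. What is at fault is a misstated analysis set and an inconsistent set of planning inputs. The stray enrolment figures are a separate and lesser matter, since 20,000 is the target used in the recruitment plan, the screening section and the sample size section.

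**What to change.** - In Section 5.1, replace the three counts with one line per arm: randomised, treated as assigned, evaluable. Use one set of crossover rates with its data cut-off date, including the current rivaroxaban rate, and use the same set in Table 1 or say why it differs.
- Recompute the Section 5.2 margins from those numbers, and say whether each refers to the whole arm or to a pairwise-eligible set.
- Give the aspirin-rivaroxaban counts (after the pairwise restriction), interval width and power beside Table 1, with the one-sided alpha stated.
- Separately, align 18,829 in Section 3.1 and 25,000 in Section 4.1.1 with the 20,000 target and its 90% figure.

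The cost is text and one table. The stated counts become less favourable. No extra patients are needed, and the margin and analysis method do not change.
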